#### Descriptive analysis of intervention content

Additional analysis will be presented at the level of the Your Choice session meetings between the young person and their practitioner. This analysis will describe various aspects of sessions, both in the control and treatment groups, including: content covered, duration, frequency and level of engagement of the young person.

#### Longitudinal follow-up analyses

The endline data will be collected at week 20 after the baseline data. This is when primary and most secondary outcomes will be measured. If we are able to secure UPN for individuals, then we will attempt to apply for an extract of the linked NPD-PNC data for the sample

covered in the efficacy trial. This will be used to provide a long-term follow-up, for both outcomes related to education and criminal offences.

#### Imbalance at baseline

We will present a table of baseline balance between treated and control groups, for all individuals recruited in the teams that were randomised and for the sample of individuals with endline primary outcome data. This will report means and standard deviations for continuous variables (and only means for binary outcomes). This will use data both the workbooks and the baseline surveys fielded to young people and practitioners. The basic characteristics to be shown are the demographic characteristics of the young person, other background characteristics of the young person (their needs, activities and support), their SDQ measures, self-assessment of risk, and those of their practitioner.

#### Missing data

We will examine the extent of missingness, the patterns of missingness, and whether it correlates to treatment assignment. First, we will specify the number of complete cases (i.e. those without any data missing) and will attempt to establish the missingness mechanism (i.e. what variables in the data are predictive of non-response). To do the latter, we will run a logistic regression model (accounting for strata fixed effects and clustering standard errors at the LA level) of an indicator taking the value 1 if a variable is missing, and 0 otherwise, on information that might be predictive of missingness. This will be done separately for outcome variables and covariates included in the headline model.

We do not propose to impute missing outcome data for our main estimates. We will follow YEF's guidance on missing data analyses and perform relevant sensitivity analyses if there is more than 10% of data missing. If covariates are missing conditional on other covariates or outcomes, we will run Multiple Imputation and compare the results with complete cases and with MI. If the results are similar, this will suggest the complete cases are unlikely to be biased (but underpowered). If the results are not similar, we will discuss implications of this analysis clearly in the report.

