data at endline in the efficacy study, which is critical for measuring the primary outcome, the endline youth survey started being administered in a regular session at the end of the programme, in the presence of the youth practitioner and with an audio facility for participants who have difficulties reading the text. This changes the practice briefly tried out at the start of the pilot period, when young people would be contacted outside regular sessions to complete the survey with the support of a peer researcher. The majority of pilot participants already filled in their endline questionnaire using the new procedure.

- Obtaining the collaboration of control teams was especially difficult given the generalised feeling among youth practitioners in these teams that there is less in the trial for them and the young people they treat. It led to lower adherence to data collection protocols among control teams. In response, the training campaign prior to efficacy trial will aim to reach SPOCs and all practitioners and emphasize the critical role of control teams for the success of the efficacy trial and future support for expansion of Your Choice in the longer term.
- Early testing suggests that the SDQ information collected at baseline is of good quality, supporting the use of a similar test at endline and for the primary outcome.
- The intervention originally projected that the delivery of Your Choice to young people would immediately follow recruitment, running between weeks 1 and 12 and delivering 3 weekly sessions over this period (calls, meetings, going to the gym, working with parent/carer for psychoeducation), each session lasting for 45-60 mins (possibly longer). The pilot demonstrated that this time schedule is difficult to keep in practice. More realistically, there is generally a gap of up to 2 weeks between recruitment and the starting of the programme, and the delivery of sessions happens over a longer time frame of 16 to 18 weeks. The programme is typically finished by the end of week 20. For that reason, the efficacy trial and the data collection exercises are designed under the assumption that the delivery of Your Choice to young people takes 20 weeks from recruitment to end. We refer to the first and last weeks in the programme as weeks 1 and 20, respectively.

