Number of participants	Due to lower-than-expected recruitment and higher than expected attrition, in January 2025 the recruitment period was extended to the end of February 2025. To inform this decision, we re-estimated the number of participants based on recruitment to date and new information from the Local Authorities and revised the number of participants down to 1,563 young people recruited across the internal pilot and efficacy trial recruited between August 2023 and end of February 2025. Across teams that have ever been randomised, this included an expected 1,402 young people recruited between August 2023 and February 2025 and 161 young people who were recruited during the internal pilot phase (82 of whom we have endline data for). We expect a 70% data completion rate across the internal pilot and efficacy trials, which sets the overall sample for impact evaluation at 1,094.		
Primary outcome and data source	Indicator for scoring in the high or very high range of the conduct problems subscale of the Strengths and Difficulties Questionnaires (SDQ). The high and very high range threshold is defined by the SDQ's four-fold categorisation.		
	The SDQ is taken at the start and end of the young person's pathway through the programme, at weeks 1 and 20 after		

	recruitment. In both cases, they are administered during a session with the practitioner, as part of the baseline and endline surveys. Some small variation in the timing of these surveys is allowed, to accommodate differing start and end dates for the programme and convenience in scheduling meetings between participants and practitioners. Below we will be referring to week 1 and 20 as expected times for these surveys.
	Criminal activity : Indicator for recorded arrest in Police National Computers during first 16 months after recruitment (allowing for 4-months treatment plus 1 year following treatment).
	Self-reported and practitioner-reported perceptions of young person's safety: Young person and practitioner versions of "Checkpoint. A safety scale for young people", which is an instrument to measure young people's perceptions of safety developed by the research team. Measured at baseline and endline as part of the participant's and practitioner's surveys (weeks 1 and 20 after recruitment, respectively).

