### Sample size calculations overview

The expected analytical sample will have two features that are important to consider for inference:

- There will be a small number of units of randomisation (teams) within strata (LA): Among the 29 LAs participating in the whole evaluation (internal pilot + efficacy), the median number of teams per LA is 3 (the average 4.6), with all but 2 LAs having 10 or fewer teams involved in the trial (Brent has 12 teams and Barking and Dagenham has 21 teams).
- Units of randomisation (teams) have more than 10 observations on average: Based on the conservative predictions of participating young people provided by Local Authorities so far, the average expected number of participants per team is 13.

De Chaisemartin and Ramirez-Cueller (2024) show that in stratified cluster RCT where the number of units of randomisation (teams) is small (10 or fewer) within strata (Local Authorities), the regular practice of clustering standard errors at the unit of randomisation can lead to downward bias in estimates of the variance of the treatment effect, resulting in over-rejecting the null hypothesis (of no effect). They advise that standard errors should be clustered at the strata level (LA) when RCTs have this type of configuration (and this result holds whether or not strata fixed effects are controlled for).

We are not aware of any software allowing us to perform power calculations that take these issues into account. In order to account for the exact nature of our dataset and for these technical complexities, we therefore opted for calculating the Minimum Detectable Effect associated with 0.8 power via simulations programmed in STATA and adapting the procedure

<sup>6 Even after removing the 6 teams that recruited in the pilot but did not collect any endline data, the median number of teams per LA is also 3 (the average if 4.5).

<sup>7 After considering the actual attrition at endline in the pilot (54%) and the expected 30% attrition rate at endline in the efficacy, we would have 9.4 observations per team on average.

<sup>8 In cases where clusters are small (fewer than 10 observations per unit of randomisation on average), estimates of the standard errors should not adjust for degrees of freedom. This is not the case we expect even under the conservative projections in terms of participating young people.

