#### Primary population of interest

The primary population of interest will be young people aged 11-18 referred to their Local Authorities for support and at medium to high risk of contextual harm.

Table 5 provides information about the number of young people and teams, and their distribution across treated and control groups, which were used to perform the power calculations. These numbers reflect the best information available at the time of writing, drawn from the Local Authorities' plans in terms of teams and expected numbers of participants in each team, before the trial started (sample A) and when the decision to extend the recruitment period was considered (Sample B).

Sample A reflects the size and composition of the final sample as estimated before the trial started. It totals 1857 young people across 138 teams.

Sample B reflects the size and composition of the final sample as re-estimated as of January 2025. It totals 1563 young people across 132 teams. This number was re-estimated based on recruitment to date and new information from Local Authorities about the number of young people they would expect to recruit if the recruitment period was extended to the end of February 2025.

		Sample A (1.0 original version)	Sample B (1.1 January 2025 update)
Average cluster size (if clustered)		Average number of participants per cluster (team): 13	Average number of participants per cluster (team): 11.8
Number of clusters (teams)	Intervention	70	83
	Control	70	49
	Total	138	132
Number of participants	Intervention	960	937
	Control	897	626
	Total	1857	1563

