#### Table 5: Structure of the two datasets used to perform power calculations

Although randomisation during the efficacy phase allocates teams to training and control on a 50-50 basis, legacy randomisation from the Home Office and pilot phases means more teams are trained than control. The power calculations reported above account for this imbalance.

Our power calculations account for a 30% attrition rate. This attrition rate is calculated based on all participants ever recruited in randomised teams in the pilot and efficacy trials (regardless of not they collected any endline data).

Table 6 report the MDE estimated using the simulation methodology described above, under the below assumptions about power, significance level and the type of test we want to perform and under different assumptions about the attrition rate and about whether Local Authority fixed effects are controlled for in the regression. Note that, when we revised the expected sample size in January 2025, we also revised our assumptions about the ICC and mean of the baseline based on estimates of these parameters in the baseline sample recruited during efficacy, which we deemed more reliable than the pilot sample due to its much greater size.

These assumptions turned out to be less conservative than those made when we initially ran power calculations: the ICC was lower (0.09 as opposed to 0.12) and the mean of the primary outcome variable was higher (0.6 as opposed to 0.3). This meant that, even though the revised sample size in scenario 2 is lower than the initial sample size in scenario 1 the MDE is slightly lower (22% instead of 24%).

Table 6: Minimum Detectable Effect on primary outcome (binary indicator for high to very high range of conduct problems) under the assumption we do not control for lagged outcome in the larger dataset

Scenario	Scenario 1: Sample A with original priors for simulation parameters (1.0 original version)	Scenario 2: Sample B with revised priors for simulation parameters (1.1 January 2025 update)
Alpha 	0.05	0.05
Power	0.8	0.8

<sup>11 Please adjust as necessary for trials with multiple primary outcomes, 3-arm trials, etc., when a Bonferroni correction is used to account for family-wise errors.

One-sided or two-sided?	Two-sided	Two-sided
ІСС	0.12	0.09
Mean of the primary outcome in control group	0.3	0.6

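### Agreement between complete cases and covariate imputation says nothing about missing primary outcomes, yet the SAP reads it as a sign that bias is unlikely

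*SAP*

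**What the plan says.** The SAP section on missing data starts with description: how much is missing, in what pattern, and whether missingness is associated with arm. Logistic models of a missingness indicator follow, run separately for outcomes and for the covariates of the headline model. Complete cases are defined as records with nothing missing.

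On handling, the section says: "We do not propose to impute missing outcome data for our main estimates". It refers to the funder's guidance and promises sensitivity analyses once more than 10% of data are missing, but names none. Multiple imputation is introduced for missing covariates, and its result is to be compared with complete cases. The reading rule is: "If the results are similar, this will suggest the complete cases are unlikely to be biased (but underpowered"). If the two differ, the report will discuss the implications.

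Elsewhere, the SAP section on baseline imbalance adds a balance table restricted to those with endline primary outcome data. The protocol's analysis steps contain no plan for missing outcomes.

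On scale, the SAP says: "Our power calculations account for a 30% attrition rate". Its front table adds: "We expect a 70% data completion rate across the internal pilot and efficacy trials, which sets the overall sample for impact evaluation at 1,094". The same table reports that attrition has run above plan, without a rate. On control teams in the pilot, the protocol's section on lessons learned says: "It led to lower adherence to data collection protocols among control teams".

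**The concern.** The losses that the documents quantify are in the endline questionnaire, which carries the primary outcome. Imputing covariates brings back young people who have an endline SDQ but lack a baseline item. It brings back nobody whose endline SDQ is missing. Any bias caused by those absences is therefore shared by the two analyses being compared, and their agreement is no evidence against it.

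A mechanism is easy to see, though not demonstrated. The endline form is completed in a session with the practitioner, so a young person who disengages from support is likely to lose the outcome too. Disengagement may be related to conduct, and differently so under intensive contact than under usual support.

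At stake is how the primary result is described. Followed as written, the rule would let the report call the complete cases unlikely to be biased on the strength of a comparison that cannot fail in the way that matters.

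**Working it through.** **1. The plan's own figures**
- Analysed sample, January 2025 revision: 1,563 × 0.70 = 1,094.1 (SAP: 1,094).
- Analysed sample, initial estimate: 1,698 × 0.70 + 83 = 1,271.6 (both documents: 1,272).
- Pilot loss: 96/179 = 53.6% (protocol counts; stated as 54%) or 79/161 = 49.1% (SAP counts; protocol Table 4 says 50%).
- Overall 30% loss means 1,563 − 1,094 = 469 missing. Of these, 79 are from the pilot, leaving 390/1,402 = 27.8% for the efficacy phase.

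**2. Who is in each analysis**
- Complete case: outcome and covariates both observed.
- Covariate imputation: outcome observed, covariates observed or imputed.
- Outcome missing: in neither.

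**3. Simulation**

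From the documents: 1,563 participants split 937:626 (SAP Table 5, Sample B), 29 LAs, outcome rate about 0.6. Assumed: true effect 0, baseline indicator missing in about 12%, and the outcome-missingness mechanisms below. The model is least squares on arm, baseline indicator and LA effects, with 400 replicates per row. Team effects were not simulated; they would change the spread, not the shared bias.

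| Assumed outcome missingness | Missing, Your Choice / control | Complete case | Covariate MI | Outcome MI under MAR | Mean absolute difference, complete case v covariate MI |
|---|---|---|---|---|---|
| Unrelated to anything | 30% / 30% | 0.000 | 0.001 | 0.001 | 0.008 |
| Arm only | 25% / 37.5% | 0.000 | 0.000 | 0.000 | 0.008 |
| Your Choice: 35% if high score, 10% if not; control: unrelated to outcome | 25% / 37.5% | −0.067 | −0.067 | −0.065 | 0.008 |
| Your Choice as above; control: 30% if high score, 49% if not | 25% / 37.6% | −0.131 | −0.130 | −0.126 | 0.008 |

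Hand check of row 3: the completers' rate in the Your Choice arm is 0.6 × 0.65/0.75 = 0.52, so the raw difference is 0.52 − 0.60 = −0.08. Row 4: control completers are at 0.6 × 0.70/0.624 = 0.673, so the raw difference is 0.52 − 0.673 = −0.153. Adjustment brings these to −0.067 and −0.131.

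**4. Size under simple assumptions**

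Let m be the missing share in an arm and g the excess prevalence in non-completers over completers that remains after baseline adjustment. Observed prevalence = overall − m × g. With the same g in both arms, bias in (Your Choice − control) = g × (m control − m Your Choice).
- 45% v 25% missing, g = 20 points: 0.20 × 0.20 = 4.0 points.
- 40% v 25% missing, g = 10 points: 0.10 × 0.15 = 1.5 points.
- 30% missing in both arms, g = 20 points in one arm only: 0.30 × 0.20 = 6.0 points in size.
- Any missing rates, g = 0: no bias.

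The first two understate a benefit; the third can go either way. The by-arm rates and the gaps are assumptions.

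Comparator: the SAP's current detectable effect is stated as 10.8 points, but 22% × 0.6 = 13.2 (10.8 is 18% of 0.6). Four points is 37% of 10.8 or 30% of 13.2.

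**5. Tipping points and bounds**

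Full-sample difference = (1 − m) × observed difference + m × difference among the missing. To bring the point estimate to zero, the missing must differ in the opposite direction by observed × (1 − m)/m:
- Observed 13.2 points: 13.2 × 0.70/0.30 = 30.8 points at 30% missing; 13.2 points at 50%.
- Observed 10.8 points: 25.2 points at 30% missing; 10.8 points at 50%.

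With 0.6 observed in both arms, worst-case bounds on the difference are ±30 points at 30% missing and ±50 points at 50%.

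**The case against.** The best defence is context. The sentence follows a clause about covariates, and comparing complete cases with imputation is informative about cases lost through missing covariates. Its wording is hedged. Outcome imputation is declined only for the main estimates, and expected losses of 30% would trigger the promised sensitivity analyses. The funder's guidance is not available here, so it may well call for analyses of missing outcomes. The headline model also adjusts for the baseline outcome and LA, so only a gap that survives adjustment causes bias.

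Much of this stands. The SAP does address missing outcomes, and its check against arm would pick up unequal completion. What does not stand is the inference. Complete cases, as the SAP defines them, exclude those without an outcome, and the sentence does not limit its conclusion to covariates. The arm check and the logistic models relate missingness to observed variables; they cannot show dependence on the outcome that was not observed. No named analysis fills that gap.

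A reader might go further and infer that the pilot showed differential endline loss. It did not: the protocol reports weaker adherence to data collection in control teams, without completion rates by arm. A reader might also infer that unequal loss is itself a bias. Row 2 of the simulation and the g = 0 case show that it is not.

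**Conclusion.** The reading rule is wrong for the missing data that matter most. With an expected 30% of primary outcomes missing, and a pilot that lost 49% to 54%, agreement between complete cases and covariate imputation carries no information on outcome-dependent missingness: the mean difference between them was 0.8 points whether the bias was 0, 6.7 or 13.1 points. Imputing the outcome under MAR would not reveal it either. Nothing in the documents shows that such bias exists or how large it is. The 4-point illustration, against 10.8 points as stated or 13.2 by the SAP's own percentage, rests on assumed missing rates by arm and an assumed residual gap. The finding is therefore a faulty inference and an unspecified sensitivity analysis, not a demonstrated bias in the primary estimate.

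**What to change.** Limit the sentence to loss of cases through missing covariates, and add that the comparison says nothing about missing outcomes.

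Name the sensitivity analysis for the primary outcome: multiple imputation of the outcome by arm as the starting point, then a delta (tipping-point) analysis that shifts prevalence among non-completers separately in each arm. Report the delta at which the conclusion changes and discuss whether it is plausible. Do not require the conclusion to survive a fixed range such as 0 to 30 points. At 30% missing, a 30-point shift in one arm moves the estimate 9 points, taking 13.2 down to 4.2 against a standard error of about 13.2/2.8 = 4.7, so even an effect at the detectable size would fail. Add bounds if completion differs by arm.

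The cost is a little more analysis on data already being collected and possibly a more cautious conclusion. The primary estimator, sample and design do not change.

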#### Compliance

Compliance will be measured at several levels: at the young person level and at the practitioner level. At the young person level – there can be full compliance/non-compliance, as well as partial compliance.

*Full compliance/non-compliance*: In the Your Choice RCT, treatment is assigned at the level of the team of practitioners. However, it may be that teams deviate from the protocol they were given young people allocated to a Your Choice trained team may receive another form of support, and young people allocated to a Business As Usual team end up receiving the Your

Choice programme if they end up being supported by a Your Choice trained practitioner from another team. If that is the case, the ITT analysis may underestimate the impact of the intervention on those who actually received it.

*Partial compliance*: the intervention is supposed to involve 3 meetings per week over the course of 12 weeks, but there can be partial compliance if young people receive a share of the designated Your Choice sessions. As with full non-compliance, in the presence of partial compliance the ITT analysis will generally underestimate the effect of the intervention among those who actually received the full treatment.

To consider these possibilities, we will use monitoring data to measure the extent of noncompliance in the treatment and the control groups and the extent of partial compliance in the treatment group. We will then test whether the characteristics of young people noncompliers are different from those of compliers in statistically significant ways.

We will further extend our analysis by using an Instrumental Variable (IV) approach to give an indication of the effects a) of receiving Your Choice and b) of the intensity of treatment. To implement a) and b), we will use a Two Stage Least Squares (2SLS) approach with group allocation as the instrumental variable for compliance. In a), we will define compliance as a binary indicator that takes the value 1 if the young person receives any of the Your Choice programme and 0 otherwise. In b), we will define compliance as a continuous variable measuring the proportion of Your Choice sessions that the young person received out of the total planned for participants (=12x3). The first stage will model the compliance variable using the same explanatory variables used for the headline ITT analyses and the instrument. The second stage model will use predicted compliance in place of the group identifier variable in the ITT analyses specified above to generate Complier Average Causal Effect (CACE) estimates.

At the practitioner level – practitioners are supposed to received 3 + 1 days of training and to receive clinical supervision at least once monthly. Using information from the workbook on training and clinical supervision sessions, we will document the extent to which this happened across teams involved in the trial. We will not take this form of compliance into consideration in the estimation of the treatment effects.

